## 11 RISK/BENEFIT ASSESSMENT

### 11.1.1 KNOWN POTENTIAL RISKS

The proposed study poses minimal risks. Potential risks that might exist fall into three categories: (a) risks associated with the intervention; (b) risks associated with research assessments, and (c) risks associated with potential loss of confidentiality. We describe each below.

**Risks of the intervention.** The intervention has no known risks. However, it is possible that for people who have misperceptions about palliative care (e.g., that it is only for people for whom cancer treatment is not working), there may be an initial negative reaction to being presented information about palliative care. It is also possible that some people may experience some mild distress when completing the palliative care needs assessment, which asks about common lung cancer symptoms and concerns (e.g., worry about family members). Both risks are expected to be rare occurrences and mild in severity.

**Risks associated with research assessments.** The instruments and methodologies are well tested and are not known to cause problems or distress on the part of the participants; however, there is the possibility that some individuals may find answering the questions distressing (e.g., asking about their palliative care knowledge) or boring. This risk is expected to be a rare occurrence and mild in severity.

**Risks associated with potential loss of confidentiality and privacy.** There is a risk of loss of confidentiality and privacy as patients may be met in person at Markey Cancer Center or receive phone/Zoom calls, emails, or MyChart® messages from the study coordinator. In addition, patients will complete research assessments using an online form in REDCap, which could possibly result in a loss of confidentiality. However, the research team will take every precaution to safeguard participant data.

### 11.1.2 KNOWN POTENTIAL BENEFITS

This study will determine whether it may be feasible to conduct a fully powered randomized controlled trial of mPal. It is also possible that patients who receive the mPal intervention may benefit from receiving education about an evidence-based intervention in cancer care (palliative care) which may impact their care and improve health outcomes. These benefits may or may not occur for any and all participants. Participants may experience some benefit from feeling that they have contributed to a study that can help inform ways to help future lung cancer patients. For society as a whole, the findings will inform future intervention development and testing with lung cancer patients. Future patients may benefit from an intervention that is low burden in terms of time and cost, potentially widely available due to delivery mode, and aligned with personal values and unmet supportive care needs.

### 11.1.3 ASSESSMENT OF POTENTIAL RISKS AND BENEFITS AND PROCEDURES TO MINIMIZE RISKS

The risk of harm or discomfort that may happen as a result of taking part in this research study is not expected to be more than in daily life or from routine physical or psychological examinations or tests. This study will determine whether the mPal tool is feasible for advanced stage lung cancer patients in primary oncology. Results of this study will inform whether an efficacy study is warranted.

### **Procedures to Minimize Risks.**

**Protection for risks associated with the intervention.** The biggest risk we perceive with the intervention is distress resulting from the education about palliative care for patients in the intervention. This risk is reduced by the assessment that is built into the mPal tool, which asks patients to select what they learned about palliative care (e.g., that it is not the same as hospice, that it can be delivered at any time or stage of disease).

**Protection for risks associated with assessment.** Patients will give voluntary responses to questions; they are told that they can decline to answer any questions that they choose. If patients express distress or frustration with the questions, study staff will remind them that these questions are voluntary and that they are meant to apply to a broad range of patients and may not necessarily reflect each person's experience. If patients remain distressed, the study PI, [name] or other qualified member of the study team will contact them. If concerns remain, participants will be directed either to the chair of the IRB to discuss their concerns about the assessments and will be referred for psychological services at the Markey Cancer Center.

**Protection for risks associated with potential loss of confidentiality.** Prior to any contact with study participants or data, the Principal Investigator will ensure study team members have completed required institutional training in maintaining confidentiality of study data. Further, all study staff will complete training in Good Clinical Practice, which is required for clinical trial research.

Assessments completed on paper will have the participant's assigned unique ID and not the participant's name on it. Assessments completed online will be done through a secure survey site, REDCap. REDCap requires HTTPS login access. Hypertext Transfer Protocol Secure (HTTPS) is a combination of the Hypertext Transfer Protocol with the SSL/TLS protocol to provide encryption and secure identification of the server. HTTPS connections are used for payment transactions on the Internet and for sensitive transactions in corporate information systems. Assessments completed on the phone with the study coordinator will be conducted at an agreed upon time by the participant when they believe they will not be interrupted. The study coordinator will complete the phone assessments from a private office. At the start of the call, the study coordinator will query whether it is a good time and whether the participant is comfortable answering questions in their current location.

Data for all participants will be kept strictly confidential, except as mandated by law. All electronic data will be kept on UK OneDrive or REDCap. Any paper documentation will be kept in locked file cabinets or a locked file room. Participants will be assigned a numerical code for identification in the files. Names and other identifiers will be kept in separate password protected files. Audio data will be stored on UK's OneDrive.

All data presentation will be of aggregate-level data; patients will not be individually named.

**Psychiatric emergencies.** In the case of psychiatric emergencies, patient care will take precedence over treatment protocol. If the study coordinator or interventionist identifies concerns about a patient's mental state, the study PI or other qualified member of the study team will contact the participant and determine whether a referral to psychological counseling is needed or whether emergency services are needed. If the patient is able to continue the study, the PI or other qualified member of the study team will develop a follow-up plan using clinical judgment based upon the data and any additional information acquired through interview. Referrals and assistance will be given in obtaining appropriate treatment for any participant terminated from the study for safety issues. Reports will be filed with all necessary governing bodies, including the University of Kentucky IRB.

## 11.2 SAFETY MONITORING AND ADVERSE EVENTS

### 11.2.1 DEFINITION OF ADVERSE EVENTS

This study is considered to carry a low risk to patients. AEs will be reported if they are study related. For example, patient hospitalization or death due to disease is expected in this population and unlikely to be an AE related to the study. However, if the AE could be related to the study (i.e., there is a temporal relationship between the study procedures and the event or reasonable possibility means that there is evidence to suggest a causal relationship between the study procedures and the AE), it will be reported as an AE. An example of an AE for this study would be severe distress during the intervention session that requires additional clinical management for safety. Any psychiatric condition that is present at the time the patient is screened and enrolled will be considered as baseline and not reported as an AE. However, if the patient's condition deteriorates during the study, it will be reported as an AE.

The PI and/or other qualified Co-I will be responsible for reviewing the AE to grade its severity (mild, moderate, severe) and relatedness (definitely, probably, potentially) to the study intervention.

### 11.2.2 MONITORING FOR AE'S AND FOLLOW-UP

Several mechanisms for monitoring the occurrence of adverse events will be employed. The study coordinator will oversee day-to-day monitoring of the study activities and will have daily contact with the PI.

There will be ongoing communication among the research team. This will be facilitated by: 1) regular (weekly or bi-weekly) meetings with project staff and investigators to discuss study progress, reactions to the intervention, and any adverse events; 2) supervision of the study coordinator, and data manager. For medical adverse events, patients will contact their oncology care team or emergency medical services as they would in routine care.

### 11.2.3 ADVERSE EVENT REPORTING

The PI or designated personnel will be responsible for reporting the results of an AE evaluation to the NIH and the IRB as soon as possible, but no later than 14 working days after the study team first learns of the event.

## 11.3 UNANTICIPATED PROBLEMS

### 11.3.1 DEFINITION OF UNANTICIPATED PROBLEMS

This protocol uses the definition of Unanticipated Problems as defined by the Office for Human Research Protections (OHRP). OHRP considers unanticipated problems involving risks to participants or others to include, in general, any incident, experience, or outcome that meets all of the following criteria:

- Unexpected in terms of nature, severity, or frequency given (a) the research procedures that are described in the protocol-related documents, such as the Institutional Review Board (IRB)-approved research protocol and informed consent document; and (b) the characteristics of the participant population being studied;
- Related or possibly related to participation in the research (“possibly related” means there is a reasonable possibility that the incident, experience, or outcome may have been caused by the procedures involved in the research); and
- Suggests that the research places participants or others at a greater risk of harm (including physical, psychological, economic, or social harm) than was previously known or recognized.

An example of an unanticipated problem would include loss of data or sensitive information due to a study laptop being stolen or a complaint from a participant or participant family member. If a participant complaint identifies a newly recognized risk, the informed consent document will be updated and previously enrolled participants will be informed of the additional potential risk.

### 11.3.2 UNANTICIPATED PROBLEMS REPORTING

The PI or designated personnel will report unanticipated problems to the IRB. This information will include a detailed description of the event, an explanation of the basis for determining that the event constitutes an unanticipated problem, and a description of any changes to the protocol or other corrective actions that have been take or are proposed in response to the unanticipated problem.

## 12 SUPPORTING DOCUMENTATION AND OPERATIONAL CONSIDERATIONS

## 12.1 REGULATORY, ETHICAL, AND STUDY OVERSIGHT CONSIDERATIONS

### 12.1.1 INFORMED CONSENT PROCESS

#### 12.1.1.1 CONSENT

For patients, written documentation of informed consent will be required prior to completing the baseline assessment and randomization. The consent form will describe the intervention, randomization, study procedures, including audiorecording of the semi-structured interviews, risks, and potential benefits.

For providers, a study cover letter will be required prior to baseline assessment. The cover letter will describe the intervention, study procedures, including audiorecording of the semi-structured interview, risks, and potential benefits.

#### 12.1.1.2 CONSENT PROCEDURES AND DOCUMENTATION

Patients will provide written informed consent through a combined consent/HIPAA release form. The consent will describe the study purpose, procedures, risks, benefits, and provide PI contact information. The consent form will describe randomization and the two potential conditions (mPal intervention or usual care). It will also describe the possibility of being asked to complete an interview and the procedures for recording the interviews. Patients will be consented in person or remotely via REDCap or paper copies through mail. When consenting patients in person, we will ensure we are meeting in a private space with the patient (e.g., physician exam room, consult room, infusion room). When consenting patients remotely, we will first ensure the patient is in a place where they have privacy and feel comfortable having a conversation. We will then review the consent form over the phone or Zoom. The consent form will be reviewed with study personnel and patients will have opportunity to ask questions. To check understanding, patients will be asked to describe their understanding of key aspects of the study (rationale, what is involved, decision not to participate not affecting their medical care) and study staff will review any aspects that do not appear to be understood. As part of the consent, all patients will be asked to consent to a HIPAA release for permission to use the following protected health information, as well as the information collected for eligibility screening:

- age
- gender
- racial/ethnic data
- zip code
- lung cancer diagnosis (includes histology and stage)
- date started lung cancer treatment
- type of treatments received
- medical record number
- ECOG/Karnofsky performance status

#### Palliative care screener results

referrals for palliative care, palliative care consultations completed, referrals to other supportive care services (e.g., Social Work), dates of referrals and consultations  
advance care planning/advance directive

A copy of the consent form will be sent with the patient on paper or electronically and retained via paper or electronically for study records.

For oncology providers, we will provide a study information sheet (cover letter). The study information sheet will be provided online (REDCap), paper, over the phone, or emailed (see protocol 55171 for precedent). If reviewed over the phone, the study team will email the participant a copy of the study information sheet and review key information verbally. Providers will have opportunity to ask questions about the study. Completion of the survey and interview will indicate implied consent. Surveys and interviews pose no more than minimal risk to the provider and involve no procedures for which consent would normally be required outside a research setting. Study information (purpose, study requirements, risks/benefits, who to contact for questions, contact information for investigators) will be provided and potential participants will be invited to contact investigators with any questions regarding the study. Potential participants can refuse to participate in this study.

---

#### 12.1.2 CONFIDENTIALITY AND PRIVACY

Confidentiality will be protected by collecting only information needed to assess study outcomes, minimizing to the fullest extent possible the collection of any information that could directly identify subjects, and maintaining all study information in a secure manner. To help ensure subject privacy and confidentiality, only a unique study identifier will appear on the data collection forms. All interactions with patients will be conducted in as private atmosphere as possible. Any collected patient identifying information corresponding to the unique study identifier will be maintained on a linkage file, stored separately from patient data. The linkage file will be kept secure, with access limited to designated study personnel. Following data collection subject identifying information will be destroyed 6 years after the closure of the study, producing an anonymous analytical dataset. Data access will be limited to study staff. Data and records will be kept locked and secured, with any computer data password protected. No reference to any individual participant will appear in reports, presentations, or publications that may arise from the study.

---

#### 12.1.3 QUALITY ASSURANCE AND QUALITY CONTROL

Quality control procedures will be implemented as follows:

**Informed consent.** Study staff will review both the documentation of the consenting process as well as a percentage of the completed consent documents. This review will evaluate compliance with Good Clinical Practice, accuracy, and completeness. Feedback will be provided to the study team to ensure proper consenting procedures are followed.

**Source documents and the electronic data.** Some data will be initially captured on source documents (see **Section 12.1.4, Data Handling and Record Keeping**), but all will ultimately be entered into the study database.

The study team will download the REDCap data after the first 5 patients have enrolled to check for errors. We will perform logic and range checks. Patient-reported data and medical record data entered by the study coordinator in REDCap will be examined for accuracy. Specifically, the study team will compare the patient-reported packet with entries in REDCap for 50% of the data. The study team will review medical record data extracted for accuracy and consult with [name] or other member of the thoracic oncology team on the protocol if there are questions about clinical data.

**Intervention Fidelity.** Consistent delivery of the study intervention will be monitored throughout the intervention phase of the study. Procedures for ensuring fidelity of intervention delivery are described in **Section 6.2.1, Interventionist Training and Tracking**.

**Protocol Deviations.** Protocol compliance will be monitored and discussed at weekly team meetings. The study team will review protocol deviations and will implement corrective actions when the quantity or nature of deviations are deemed to be at a level of concern.

Should independent monitoring become necessary, the PI will provide direct access to all trial related sites, source data/documents, and reports for the purpose of monitoring and auditing by the sponsor/funding agency, and inspection by local and regulatory authorities.

---

#### 12.1.4 DATA HANDLING AND RECORD KEEPING

---

##### 12.1.4.1 DATA COLLECTION AND MANAGEMENT RESPONSIBILITIES

Data sources include:

- information from the electronic medical record (e.g., patient eligibility screening and upon enrollment demographic, clinical, referral data; electronic only)
- audio recorded exit interviews and transcripts (electronic; patients and providers)
- surveys (electronic or paper; patients and providers)
- participant tracking (e.g., upcoming appointments; withdrawal; discontinuation; electronic)
- refusal and withdrawal forms (electronic; patients and providers)

- preferred contact information for payment (electronic or paper; patients and providers)
- study administration/tracking logs (electronic; study staff completes; e.g., payment logs, final study statutes)

All data except for audiofiles and transcripts will be stored in REDCap, a secure electronic data capture system, or Excel behind a UK firewall on a study-specific shared drive. REDCap provides a real-time record of any changes made to data.

Patient-reported outcome data will be collected via mail, telephone, or in-person. Based on our prior studies, we anticipate that most patients will complete the assessments in-person with the study coordinator when they are at the Markey Cancer Center for other oncologic appointments.

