## 6.2 FIDELITY

### 6.2.1 INTERVENTIONIST TRAINING AND TRACKING

Because the primary component of this intervention is a web-based multicomponent tool, interventionist training and fidelity monitoring procedures are minimal. [name] (PI) and the study team will conduct an in-person training with review of procedures and role plays. [name] or another study team member will observe the first 2-3 patient intervention sessions in clinic and additional sessions as needed. The study coordinator who meets patients in clinic to show them the mPal tool will attend weekly team meetings to receive supervision.

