## 6.3 MEASURES TO MINIMIZE BIAS: RANDOMIZATION AND BLINDING

This is a randomized controlled trial design (patient-level randomization). Study staff and patients will not be blinded to allocation; however, study staff and patients will not know allocation until after a patient has completed the baseline questionnaire. The statistician will generate the randomization table, which will be implemented through REDCap.

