## 9 STUDY ASSESSMENTS AND PROCEDURES

## 9.1 ENDPOINT AND OTHER NON-SAFETY ASSESSMENTS

**Screening.** We will build a master list form in REDCap linking patient names, MRNs, and study IDs. We will build a separate REDCap form for screening. The eligibility screening form will include patient screener ID, date screened, date must be enrolled by (21 day window), eligibility criteria (e.g., performance status, time on cancer treatment, age, etc.), whether the patient is being rescreened for eligibility, and, if rescreened, the last date of screening. If deemed potentially eligible, additional fields will appear in the eligibility database for tracking dates of upcoming appointments and contact with patients. Patients must be enrolled within 21 days of screening or else they will need to be rescreened.

**Administration of Questionnaires.** Patient-reported measures related to a future efficacy trial and of treatment processes were chosen based on their validity and sensitivity to change in cancer patients and recommendation for clinical trials. These measures will be completed by patients pre-intervention (TP0), ~4 weeks after baseline (T1), and post-intervention (~8-weeks after T0; TP2) on paper, online (REDCap), or by phone. For patients who use MyChart®, a link to the REDCap survey will be provided through a study research message delivered in MyChart®. Patients will use a participation ID on their questionnaires. If more than 30 days pass between baseline and participant viewing the mPal tool, key sections (e.g., palliative care knowledge, palliative care use) of the baseline questionnaire will be re-administered prior to viewing mPal. See **Table 2** for a list of measures to be administered, psychometric properties, assessment schedule, and role in analysis plan. All patient-reported measures will be entered in REDCap in the REDCap project built for those patients who enroll.

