**Interviews.** Patients assigned to mPal (n = 20-40) will complete two interviews. The interviews will last approximately 10-15 minutes and will query overall satisfaction with the intervention, perceived impact of mPal on clinical care, and reasons patients chose or chose not to talk with their doctor about their palliative care needs. The interviews will take place over the phone, Zoom, or in-person, according to patient preference. Interviews will be conducted by the study team and audiorecorded. After each interview, the interviewer will write up observations in the form of field notes, which will include information about the setting (e.g., details about room if in-person vs. on the phone), personal environment (e.g., respondent's attitude and openness), social environment (e.g., presence of caregiver or others in room), and summary of patient's responses. Recordings will be transcribed verbatim, the transcripts checked for accuracy and deidentified.

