### 10.4 STATISTICAL ANALYSES

#### 10.4.1 GENERAL APPROACH

We will use descriptive statistics (means, standard deviations, median, range) to examine the distribution of continuous variables. We will calculate 95% CIs for each of the feasibility measures to determine the range of estimates that are consistent with our data.

We will use one-sample negative binomial probabilities and tests of binomial proportions to compare to hypothesized values. We will summarize reasons for ineligibility and refusal and compare patients who drop out or do not adhere by demographic and clinical characteristics. Ordinal scaled variables such as feasibility and acceptability will be compared between groups

before and after baseline (as well as change from baseline) using the Wilcoxon Rank Sum statistic. Within group comparison of the pre versus post baseline measures will be evaluated using the Wilcoxon Signed Rank statistic.

We will use qualitative methods to analyze patient and provider feedback from the exit interviews and descriptive statistics to summarize participants' acceptability, feasibility, and appropriateness ratings of the intervention. The interviews will be transcribed verbatim and managed in ATLAS.ti or other qualitative software for analysis. The PI and study coordinator will code interviews by domains (e.g., perceived impact of mPal on clinical care, barriers, facilitators to using mPal, suggested changes to improve equity of mPal). Data will be analyzed using thematic content analysis to describe perceptions.

Statistical significance will be indicated by  $p < .05$ .

---

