#### 10.4.2 ANALYSIS OF THE PRIMARY ENDPOINT(S)

The primary outcome of the feasibility is enrollment ( $\geq 60\%$ ). A one-sample binomial test will be used to compare the observed enrollment percentage to 60%.

Enrollment (primary): Number of patients enrolled divided by the number of eligible patients approached

Retention: The percentage of patients and providers who complete baseline and follow-up questionnaires.

Acceptability: Mean post-treatment patient and provider ratings  $\geq 3.5/5$  on intervention acceptability, feasibility, and appropriateness (psychometrically validated measure; Table 2), and a brief semi-structured interview to explore factors associated with acceptability.

---

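### The coordinator who shows patients mPal is also expected to be present for most of their assessments, so patient ratings at T1 and self-reported outcomes at T2 are open to courtesy bias

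*Combined protocol and SAP*

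**What the plan says.** Section 6.2.1 identifies who delivers the patient tool in clinic: "The study coordinator who meets patients in clinic to show them the mPal tool". Section 12.1.4.1, citing the team's earlier studies, says of patient-reported outcomes that "we anticipate that most patients will complete the assessments in-person with the study coordinator". Section 6.3 states that "Study staff and patients will not be blinded to allocation", with one safeguard: staff and patients "will not know allocation until after a patient has completed the baseline questionnaire".

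Table 2 schedules the feasibility (FIM) and acceptability (AIM) measures for mPal patients at T1 and for providers at T3; usual-care patients do not give these ratings. Its note ties patient T1 to viewing the app or the knowledge check. Section 10.4.2 sets the benchmark as "Mean post-treatment patient and provider ratings" of at least 3.5 out of 5. Palliative care knowledge and motivation are self-reported at T0 and T2 in both arms (and at T1 in mPal only), and section 10.4.3 compares the changes between arms by t-test.

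Section 9.1 allows questionnaires "on paper, online (REDCap), or by phone". Section 11.1.3 describes telephone assessments as done with the study coordinator. No section requires that ratings be completed in private, that the mode be recorded, or that results be examined by mode.

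**The concern.** A patient who rates a tool in the presence of the person who showed it may rate it more kindly than in private. The T1 ratings have no comparator, so any such shift goes straight into the mean that is set against 3.5.

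At T2 there is a comparator, but exposure to staff is unequal. mPal patients may view the tool with staff, take the screener again up to three times, and give two interviews; usual-care patients do none of this. If courtesy grows with contact, it would appear as a difference between arms. Attitude items are more exposed than factual ones.

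At stake are the patient feasibility and acceptability conclusions and the preliminary effectiveness signal carried into the planned trial.

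**Working it through.** **Tracing the roles.** Three facts combine: the coordinator shows the tool (6.2.1), the coordinator is expected to be there for most assessments (12.1.4.1), and allocation is known once baseline is done (6.3). T0 is therefore protected; T1 and T2 are not. That one individual fills both roles is an inference from the shared job title.

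**No plan figure to reproduce.** Section 10.2 bases the 80 patients on estimating feasibility proportions and means, and gives no SD, precision target or formula. The calculations below are illustrations on stated assumptions.

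**Patient ratings against 3.5.** From the plan: 40 mPal patients and a benchmark of 3.5. Assumed: SD, true mean and shift.

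P(observed mean ≥ 3.5) = 1 − Φ((3.5 − true mean − shift) / (SD/√n))

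With SD 0.8 and n = 40, the standard error is 0.8/√40 = 0.126.

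- True mean 3.3, no shift: z = 0.2/0.126 = 1.58, probability 6%.
- True mean 3.3, shift +0.2: z = 0, probability 50%. This is 50% by construction, because the shift equals the gap to the benchmark.
- True mean 3.3, shift +0.3: z = −0.79, probability 79%.
- True mean 3.8, no shift: z = −0.3/0.126 = −2.37, probability 99%. A shift cannot change much here.

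Sensitivity to the assumed SD and to the number of raters (24 is 60% of 40, the retention target applied to the mPal arm):

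| Raters | SD | True 3.3, no shift | True 3.3, +0.2 | True 3.3, +0.3 | True 3.8, no shift |
|---|---|---|---|---|---|
| 40 | 0.6 | 2% | 50% | 85% | 99.9% |
| 40 | 0.8 | 6% | 50% | 79% | 99% |
| 40 | 1.0 | 10% | 50% | 74% | 97% |
| 24 | 0.6 | 5% | 50% | 79% | 99% |
| 24 | 0.8 | 11% | 50% | 73% | 97% |
| 24 | 1.0 | 16% | 50% | 69% | 93% |

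**T2 comparison between arms.** Suppose there is no true effect, but mPal answers carry a shift of d standard deviations of the change score. With a two-sided 5% test (the plan gives p < .05 without sidedness) and a normal approximation:

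P(reject) = Φ(d/√(2/n) − 1.96) + Φ(−d/√(2/n) − 1.96)

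At 40 per arm, √(2/40) = 0.224. For d = 0, 0.2, 0.3 and 0.5 the result is 5%, 15%, 27% and 61%. At 24 per arm, √(2/24) = 0.289, and the result is 5%, 11%, 18% and 41%.

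**The case against.** The best defence is that in-clinic assessment is deliberate. Section 5.6 lists it as a retention measure, and retention is itself a feasibility outcome. Patient education cannot be blinded, and allocation is already concealed until baseline is complete. The 3.5 benchmark is a hypothesised value with no stated go/no-go rule. Section 4.2 disclaims formal effectiveness hypotheses, and the chief goal in 10.4.3 is to estimate standard deviations, which a constant shift would leave unchanged. Some patients will view mPal at home (6.1.1) or answer by REDCap link (9.1). The documents do not show that any shift will occur. All of this stands and limits the weight of the point. It does not remove it, because private completion is compatible with the same clinic visits.

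Four stronger readings are tempting, and the documents do not support them.

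- **That the coordinator administers or explains the questionnaires.** Section 12.1.4.1 speaks of completing them in person with the coordinator and lists surveys as electronic or paper. This can mean self-completion with staff nearby. Only telephone completion is clearly run with the coordinator.
- **That interview coding inflates the scores.** Section 10.4.1 says "The PI and study coordinator will code interviews by domains", but coding transcripts cannot move a rating or a T2 questionnaire score.
- **That every 3.5 benchmark is affected.** The expectation of in-person completion concerns patients, not providers.
- **That 12.1.4.1 leaves out online surveys.** Its list of data sources includes electronic surveys, so the lists of modes in 9.1 and 12.1.4.1 need only a wording alignment.

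**Conclusion.** The point holds for patient FIM and AIM ratings at T1 and for self-reported palliative care knowledge and motivation at T2. It does not reach enrolment, provider ratings or referrals extracted from the health record.

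Its size depends on unknowns. If true patient ratings lie just below 3.5, a shift of 0.2 to 0.3 points can turn a likely miss into an even or better chance of success. If they are near 3.8, the criterion is met 93% to 99.9% of the time without any shift, so the conclusion would seldom change. At T2, a shift of 0.2 to 0.3 SD confined to mPal would raise the false-positive rate from 5% to about 15% to 27% at 40 per arm. SD, true mean and shift are all assumptions. More patients would not remove the bias.

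This is an inexpensive improvement worth making, not a flaw in the primary analysis.

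**What to change.** In 9.1 and 12.1.4.1:

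1. Make private self-completion the default for patient FIM, AIM, palliative care knowledge and motivation at T1 and T2, in each arm where the measure is scheduled. Use a REDCap link, or a tablet or paper form handed over in clinic and completed without the coordinator reading or watching.
2. Use read-aloud or telephone completion with the coordinator only when the patient asks or cannot self-complete.
3. Complete FIM and AIM before the T1 interview.
4. Record the mode in one REDCap field and report ratings by mode. This is descriptive, since patients are not randomized to mode.
5. Align the wording of the two lists of modes.

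The cost is procedure wording and one data field. REDCap, tablets and paper are already in the plan, no staff are added, and the clinic visits that support retention stay. Expect slightly more skipped items or reminders. The greater staff contact in the mPal arm remains, so the change reduces the bias and may not eliminate it.
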